7.1.2. Possible lasting adverse effects

At high doses of LSD, and in rare cases, flashback phenomena psychotic reactions have been reported. Negative experiences (bad trips) and flashback phenomena may occur, generally in uncontrolled conditions and when high doses of LSD are used (Strassman, 1984).

7.1.3. Venipuncture

There is a risk for pain, bruising and thrombophlebitis due to venipuncture.

7.2 LSD-Specific Toxicity Considerations

The primary safety concerns with hallucinogen research are psychological rather than physiological in nature (Johnson et al., 2008). Even under unsupervised and unprepared conditions, reactions to hallucinogens involving violence or self-destructive behavior are rare, and it is important not to create an unrealistic account of the dangers of hallucinogens (Johnson et al., 2008). Nonetheless, even infrequent reports of such dangers require that we take seriously such risks and take steps to avoid their occurrence. Subjects must receive the first dose of MM-120 in the clinic under supervision to assess for unusual or exaggerated responses and should be taken under direct supervision of study personnel to avoid substance deviation. For home medication, study medication under the Investigator's supervision may be administered at home to the subject to assure study medication compliance and safety and perform all protocol

procedures including AE/SAE, concomitant medication, and C-SSRS assessment. Subject cannot drive or operate heavy machinery or do anything else that would be dangerous in an impaired state for the remainder of the day after receiving IMP.

7.2.1. Psychological effects

There is currently no evidence for positive or adverse psychological effects from controlled studies on repeated low dosing LSD. Survey studies among persons performing repeated low dosing explored concerns relating to adverse effects. Reported concerns were stronger-than-expected psychedelic effects, anxiety, and physical adverse side effects (Lea et al., 2020). Other perceived limitations include issues related to dosing, taking illegal substances, limited or no mental health or cognitive improvement, unpleasant “off” days, only short-term benefits, and concerns about dependence and drug-related risks (Lea et al., 2019). In the present study, the first dosing will be under full supervision at the research sites. The use of MM-120 as study medication will be legal, and the administration of the substance will always be by the study personnel or observed by study personnel through a video conference, and as pure substance in a precisely known dose. At the dose used, MM-120 should not produce relevant autonomic system stimulation based on previous studies. However, it is possible that MM-120 will not produce an improvement of ADHD symptomatology, and may not be effective overall, and may even worsen symptoms in some subjects. This will be tested in the present study.

When used at high doses, LSD and other psychoactive substances induce mild or moderate anticipatory anxiety at the beginning of the onset of the drug effect (Griffiths et al., 2006; Liechti et al., 2001; Schmid et al., 2015). Any such reactions are expected to resolve spontaneously with supportive care by the investigators (Griffiths et al., 2011; Griffiths et al., 2006; Schmid et al., 2015). At the dose of MM-120 to be used in the present study, subjects are expected to retain their thought control, and in contrast to psychotic subjects, subjects will remain aware of the transient state of the drug-induced experience if they should at all realize any change. Events of more pronounced anxiety, panic attacks or agitation are highly unlikely to occur. In the case of any psychiatric complications after the study session, and also if the subjects would like to discuss negative experiences in association with the study, they can contact the study physician, who will offer further assistance beyond the testing days.

7.2.2. Self-injurious behavior

People who have taken LSD in uncontrolled settings may engage in reckless behavior, such as driving while intoxicated. This risk is greatly reduced by the use of very low doses of LSD. In the current study, subjects will take MM-120 under supervision, and remain at the study site for the first dosing to assess for any unusual or exaggerated effects, and when the dose is given at home it will be under the supervision of the investigator to assure compliance and safety. Prolonged psychiatric symptoms and/or psychosis after low dose LSD are rare reactions that are unlikely to occur at the dose used in this study, and particularly in the cohort of non-psychotic subjects to be included in this study. LSD may trigger psychotic episodes in people already vulnerable to psychosis rather than directly causing it.

7.2.3. Columbia-Suicide Severity Rating Scale

The Columbia-Suicide Severity Rating Scale (C-SSRS) is a validated outcome assessment that assesses a subject's suicidal ideation or behavior over a specified time interval (Posner et al., 2011). Suicidal ideation is assessed on a scale from 1 (wish to be dead) to 5 (active suicidal ideation with specific plan and intent). Suicidal behavior is assessed based on responses to individual prompts about prior suicidal actions. The C-SSRS will be assessed at all study visits.

7.2.4. Reproductive and developmental risks

There are mixed results from preclinical studies evaluating reproductive toxicity, chromosomal aberration, and mutagenic studies (refer to the MM-120 Investigator's Brochure for details). Thus, to participate in this study, women of childbearing potential (WOCBP) (i.e., physiologically capable of becoming pregnant) must agree to use a highly effective method of contraception for the duration of the study, and non-sterilized men who are sexually active with a WOCBP must agree to use barrier contraception (e.g., condom with or without spermicidal cream or jelly). Subjects who do not agree to these conditions are not eligible to participate in the study.

Appendix 2 provides definitions of WOCBP and highly effective methods of contraception as well as information about unacceptable methods of contraception. Subjects will be provided with information on acceptable methods of contraception as part of the informed consent process and will confirm when they sign a consent form that they understand the requirements for avoidance of pregnancy in the subject or the subject's sexual partner during the course of the study.

Additional Information for Female Subjects

WOCBP may participate in the study only if they have a negative urinary pregnancy test (beta human chorionic gonadotropin [β -HCG]) result at specified visits prior to dosing (i.e., Screening [Visit 1] and Day 1) and every 2 weeks during the dosing phase of the study (through Week 6).

Female subjects who are currently or planning to become pregnant or breastfeed during the study period are excluded. If a female subject withdraws early from the study, she should be advised not to become pregnant or breastfeed for 3 months after last dose of study drug. Any subject that becomes pregnant after Day 1/Dose through Week 6 is required to withdraw from the study. The subject will be monitored for the outcome of the pregnancy, and reporting will occur as described in Section 7.8.

Additional Information for Male Subjects

Male subjects should be encouraged to advise any WOCBP who are their sexual partners to use a highly effective method of contraception in addition to the male subject's use of barrier contraception. A female condom and male condom should not be used together.

Male subjects who are planning to donate sperm during the study period are excluded. If a male subject withdraws early from the study, he should be advised not to donate sperm for at least 28 days after he received the study drug.

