6. COLLECTION OF STUDY VARIABLES

6.1 Schedule of Events

The study assessments are described in the sections below and the timing of these assessments are detailed in the study plan.

Table 3: Schedule for study specific assessments

Time in Weeks	Screening	Baseline ^g	Dosing begins	Dosing Period (20 µg MM-120) ^h 6-week Blinded Treatment				End of Study/ Early Termination ^h
Arm 1 - placebo Arm 2 – MM-120	Up to 4 weeks prior to Day -1	Day -1	Day 1	Week 2 (Pre-dose on 3rd dosing visit) Day 8 (+/- 1 day)	Twice weekly* Dosing (+/- 1 day) (Starts Day 1)	Every 2 weeks (first dose of the week) (Starts Day 15)	Week 6 (before final dose unless otherwise noted)	Week 10 follow-up or final visit if withdrawing from study
Informed consent	X							
Demography	X							
Medical/surgical history	X							
Inclusion/exclusion criteria	X	X						
Pregnancy test (for women without documentation of sterilization)	X		X		X ⁸			X
Physical examination	X						X	X
Weight and BMI ^a	X						X	X
Height	X						X	X
Vital signs ^b	X	X	X		X		X	X
Clinical Laboratory Tests ^c	X					X	X	X
Pharmacokinetics			X ⁷					

Pharmacodynamics (5D-ASC, & MEQ30) ^d			X				X ^{1,5}	
12-lead ECG ^e	X			X ⁴			X ⁴	
Cognitive Performance Test		X					X	
CAARS ^f	X	X				X	X	X
ASRS (done prior to dosing)		X				X	X	X
AISRS, CGI-S	X	X			X		X	X
MINI	X							
C-SSRS screening/baseline	X							
C-SSRS since last visit (SLV)		X	X			X	X	X
VAS				X ⁶				
Check daily diary	X	X	X			X	X	X
Randomization				X				
MM-120 or placebo administration				X		X ³		
Adverse events	X	X	X			X	X	X
Concomitant medication	X	X	X			X	X	X

Abbreviations: 5D-ASC = 5 dimensions of altered states of consciousness scale; AISRS = Adult ADHD Investigator Symptom Rating Scale; ASRS = Adult ADHD Self-Report Scale; BMI = body mass index; BP = blood pressure; CAARS = Conners' Adult ADHD Rating Scale; CGI-S = Clinical Global Impression Scale; C-SSRS = Columbia-Suicide Severity Rating Scale; ECG = electrocardiogram; MEQ30 = Mystical Experience Questionnaire (30-item); VAS = Visual Analog Scale.

* Twice weekly dosing will occur every 3 to 4 days (e.g., every Monday and Wednesday) with a \pm 1 day window and will be coordinated to occur at the same time as the Week 2 visit and the every 2 weeks visits when possible.

- a Body mass index will be calculated using body height at screening.
- b Vital signs (pulse, BP, HR, RR, and body temperature) will be performed at every visit.

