- c Clinical laboratory samples for chemistry and hematology and urine samples for drug screen and pregnancy testing will be collected pre-dose.
- d Pharmacodynamic scales are completed at home up to 6 hours after dosing.
- e Subject should be supine for 5 minutes prior to ECG collection.
- f CAARS-O-RS conducted at screening. All other assessments will be with the CAARS-L-SR.
- g Baseline visit is within 3 days of Day 1 (\pm 1 day).
- h Following day 1 dosing, all visits may be conducted remotely per Investigator decision as long as all activities can be conducted per protocol, e.g., calibrated blood pressure cuff, calibrated weight scale, ECG, computer cognitive scale. Any visit conducted remotely due to COVID-19 requires Sponsor Medical Monitor and operations team notification and conduct under urgent safety measures and all protocol deviations captured in EDC designated COVID-19 deviation.

X¹ subject fills out forms at home.

X² [REDACTED] 6 weeks of blinded treatment on MM-120 / placebo; may be dosed at home per Investigator decision.

X³ 2 hours after dosing.

X⁴ 6 hours after dosing.

X⁵ Collected repeatedly 0-6 hours after dosing.

X⁶ PK samples will be collected at pre-dose, 0.5, 1, 2, 3, 4, and 6 hours post-dose.

X⁷ During treatment period, pregnancy testing will occur predose at each dosing visit or a minimum of once weekly.

Subjects excluded during screening may be rescreened once in consultation with the Sponsor's Medical Monitor, when the reason for meeting an exclusion is likely to resolve (e.g., the subject had an exclusionary acute infection that is resolving, or a medication taper is taking longer than 28 days). If a subject is rescreened, the subject must be reconsented to participate in the study.

D-LYSERGIC ACID DIETHYLAMIDE (LSD) D-TARTRATE (MM-120)
Protocol MMED007

Mind Medicine, Inc.

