6.2.4.2 Twice weekly dosing

Dosing (placebo/MM-120) must be completed by a trained study personnel with delegated authority for drug dispensing/ dosing. At each visit, adverse events and concomitant medications will be recorded, vital signs, C-SSRS (Since Last Visit) administered, and daily diary checked. Pregnancy testing will occur predose at each dosing visit or a minimum of once weekly.

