6.2.4.3 Every 2 weeks prior to first dose of the week

At each visit that occurs every 2 weeks, clinical laboratory tests, ASRS and CAARS-L-SR, and pregnancy test will be conducted. [REDACTED]

[REDACTED] When combined with a dosing visit, regular activities scheduled to be conducted at each dosing visit will also be completed (see Section 6.2.4.2).

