Abbreviations: 5D-ASC = 5 dimensions of altered states of consciousness scale; AISRS = Adult ADHD Investigator Symptom Rating Scale; ASRS = Adult ADHD Self-Report Scale; BMI = body mass index; BP = blood pressure; CAARS = Conners' Adult ADHD Rating Scale; CGI-S = Clinical Global Impression Scale; C-SSRS = Columbia-Suicide Severity Rating Scale; ECG = electrocardiogram; MEQ30 = Mystical Experience Questionnaire (30-item); PGX = pharmacogenomics; VAS = Visual Analog Scale.

\*Twice weekly dosing will occur every 3 to 4 days (e.g., every Monday and Wednesday) with a  $\pm$  1 day window and will be coordinated to occur at the same time as the Week 2 visit and the every 2 weeks visits when possible.

- a Body mass index will be calculated using body height at screening.
- b Vital signs (pulse, BP, HR, RR, and body temperature) will be performed at every visit.
- c Clinical laboratory samples for chemistry and hematology and urine samples for [REDACTED] and pregnancy testing will be collected pre-dose.
- d Pharmacodynamic scales are completed at home up to 6 hours after dosing.
- e Subject should be supine for 5 minutes prior to ECG collection.
- f CAARS-S-OR conducted at screening. All other assessments will be with the CAARS-L-SR.

g Baseline visit is within 3 days of Day 1 ( $\pm 1$  day).

h Following day 1 dosing, all visits may be conducted remotely per Investigator decision as long as all activities can be conducted per protocol, e.g., calibrated blood pressure cuff, calibrated weight scale, ECG, computer cognitive scale. Any visit conducted remotely due to COVID-19 requires Sponsor Medical Monitor and operations team notification and conduct under urgent safety measures and all protocol deviations captured in EDC designated COVID-19 deviation.

X subject fills out forms at home.

█

X 6 weeks of blinded treatment on MM-120 / placebo; may be dosed at home per Investigator decision.

X 2 hours after dosing.

X 6 hours after dosing.

X Collected repeatedly 0-6 hours after dosing.

X PK samples will be collected at pre-dose, 0.5, 1, 2, 3, 4, and 6 hours post-dose.

X During treatment period, pregnancy testing will occur predose at each dosing visit or a minimum of once weekly. All pregnancy test results are being recorded on the subject's source document (paper record). The pregnancy test results are not entered into the eCRF for weeks 3, 5, and 6.

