### **8.6 COMPLIANCE WITH STUDY TREATMENT**

The IMP will be administered at the clinic under supervision of study personnel (i.e., the Investigator or delegate) and cannot be provided to the subjects to take home.

Compliance with treatment (%) will be always 100% if treatment is administered at each visit (12 in total), from Week 1 D1 to Week 6 D40.

Study treatment is considered administered if answered 'Yes' to the question "LSD / Placebo administered?" in the "Study Drug Administration" CRF section. Study drug administration will be collected at each visit.

If Compliance with treatment (%) is different from 100%, it will be derived according to the following formula:

Total compliance (%) = (Total number of doses taken / Total number of expected doses) x 100\*,  
where:

*Total number of doses taken = Total number of expected doses – Total number of missed doses.*

*Total number of expected doses = 12 (number of doses to be administered at all 12 visits).*

*Total number of missed doses = number of doses not administered (study treatment is considered NOT administered if answered 'No' to the question "LSD / Placebo administered?" in the "Study Drug Administration" CRF section).*

In case of “Special Situation” at any visit (answer to “Were there any special situation with the study drug?” is [Yes]), the compliance will be not calculated, and the following information will be provided:

- Number of subjects with at least one Special Situation;
- Number of Special Situations;

and number of patients with ticked box 'Yes' to any of the following:

- Medication error or incorrect drug administration;
- Overdose (exceeds the protocol-specified maximum);
- Deliberate abuse;
- Deliberate misuse;
- Drug interaction;
- Occupational exposure.

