### ***8.11.3.2 Chemistry***

- Albumin;
- Total protein;
- Alkaline phosphatase;
- ALT;
- AST;
- Bilirubin, total;
- Chloride;

- Creatinine;
- Creatinine clearance (CKD-EPI);
- FSH (follicle stimulating hormone);
- GGT (gamma-glutamyl transferase);
- C Reactive Protein;
- Glucose;
- Lactate dehydrogenase;
- Blood urea nitrogen or urea;
- Phosphate;
- Potassium;
- Calcium;
- Sodium.

In addition, a [REDACTED] and a urine pregnancy test, only in women, will be performed at selected time points (Baseline, Week 2, Week 4, Week 6, Week10) before IP dosing throughout the study (see Section 2.1.2).

The definitions of marked abnormalities in SI units are provided in Table 5 and Table 6 below.

The columns labelled "L", "LL", "H" and "HH" display the increasing grade (severity) of abnormally low ("L", "LL"), or high values ("H", and "HH") for each of the laboratory parameters listed in the first column, as appropriate.

Treatment-emergent MLAs are those occurring after the study treatment start and up to study treatment discontinuation, that were not present at baseline in the same or worse category (considering the direction of worsening). In other words, the MLAs are evaluated independently by direction of worsening (e.g., a post-baseline MLA of "HH" is considered treatment-emergent if the baseline is "L" or "LL" (where applicable) or "H", or within normal limits or missing. On the other hand, it is not considered as treatment-emergent if the baseline is "HH" when applicable).

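### The current protocol states two different pregnancy-test frequencies during dosing, and the SAP's time points do not line up with what the database will hold

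*Protocol*

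**What the plan says.** **Protocol.** Section 7.2.4 makes participation of women of childbearing potential conditional on a negative urine test at Screening, on Day 1 "and every 2 weeks during the dosing phase of the study (through Week 6"). Section 6.2.4.2, on the twice-weekly dosing visits, says: "Pregnancy testing will occur predose at each dosing visit or a minimum of once weekly". The Schedule of Events footnote in 6.1 gives the same rule: "During treatment period, pregnancy testing will occur predose at each dosing visit or a minimum of once weekly". Section 6.2.4.3 adds: "At each visit that occurs every 2 weeks, clinical laboratory tests, ASRS and CAARS-L-SR, and pregnancy test will be conducted". The schedule describes those visits as "Every 2 weeks (first dose of the week) (Starts Day 15"). In the schedule table the pregnancy-test row is marked under twice-weekly dosing, not under the every-2-weeks column.

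**SAP.** The Table 1 footnote repeats the weekly minimum and says all results are kept on paper source, but "The pregnancy test results are not entered into the eCRF for weeks 3, 5, and 6". Appendix D, item 10, declares that those weeks will not be analysed. Section 8.11.3.2 says that a redacted test and the urine pregnancy test "will be performed at selected time points (Baseline, Week 2, Week 4, Week 6, Week10"). Table 2 gives pregnancy-test target days of 15 (labelled Week 2) and 29 (labelled Week 4), and has no Week 6 row. Table 3 calls the same two days Week 3 D15 and Week 5 D29. The planned output is a listing.

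**The concern.** A pregnancy between Day 1 and Week 6 requires withdrawal (Protocol 7.2.4 and 14.4). The interval between tests therefore bounds how many doses can be given before a pregnancy is found. Section 7.2.4 gives mixed preclinical reproductive findings as the reason for these controls. A site that reads only that section has textual support for testing less often than the schedule requires.

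The SAP point is separate and smaller. A reader of the pregnancy-test listing will see some dosing weeks and not others. The time points named in 8.11.3.2, the windows in Table 2 and the weeks said to be captured do not obviously describe the same set of tests.

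**Working it through.** No sample-size, power or alpha figure is involved, and the plan states no number to reproduce. The check is a count of tests and doses on the SAP's own calendar.

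**Inputs**
- Dosing days, from SAP Table 3 and 10.12.1.1: 1, 5, 8, 12, 15, 19, 22, 26, 29, 33, 36, 40. That is 12 visits, two per study week. SAP 8.6 gives the same total: "Compliance with treatment (%) will be always 100% if treatment is administered at each visit (12 in total), from Week 1 D1 to Week 6 D40".
- Every-2-weeks visits start on Day 15 (Protocol 6.1).
- Tests are pre-dose, so doses between two tests are those given from the first test day up to, but not including, the second. Visit windows of 1 day either way and missed visits are ignored.

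**Tests after Day 1**
- Each dosing visit: 12 − 1 = 11.
- Weekly minimum: 6 study weeks − the week containing Day 1 = 5.
- Every 2 weeks from Day 15: Days 15 and 15 + 14 = 29. The next would be 29 + 14 = 43, after the last dose on Day 40. That gives 2 tests, or 3 if the wording about Week 6 in 7.2.4 is read as adding a test in that week.

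**Longest gap and doses between tests**

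| Rule | Example of longest gap | Days | Doses in between |
|---|---|---|---|
| Weekly, tests 7 days apart | Day 8 to Day 15 | 7 | 2 (Days 8, 12) |
| Weekly, one test per study week | Day 1 to Day 12 | 11 | 3 (Days 1, 5, 8) |
| Every 2 weeks | Day 15 to Day 29 | 14 | 4 (Days 15, 19, 22, 26) |

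**Database capture**
- Weeks not entered: 3, 5 and 6, which is 3 of 6 dosing weeks.
- On Table 3's labels these hold Days 15, 19, 29, 33, 36 and 40, which is 6 of 12 dosing visits. Days 1, 5, 8, 12, 22 and 26 remain.
- Table 2's target days, 15 and 29, both fall in uncaptured weeks on those labels. On Table 2's own output labels the same days are Weeks 2 and 4, which are captured. The footnote does not say which labelling it uses.

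**The case against.** The strongest reply is that the rules are compatible and the protocol says where timing is set. Sections 6.1 and 8 both send the reader to the schedule, and the schedule carries the weekly minimum. A site that tests weekly, including at the every-2-weeks visits, satisfies every passage. Section 6.2.4.3 is not a rival rule: it says the regular dosing-visit activities are also done when the visits coincide, and cross-refers to 6.2.4.2. That stands. It narrows the conflict to 7.2.4 against the schedule and 6.2.4.2, and to sites that rely on 7.2.4 alone.

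A reader might infer that the SAP plans to analyse a Week 6 result it will not have. The text does not support that. Section 8.11.3.2 speaks of tests being performed, shares its list of time points with a redacted test, and is compatible with a Week 6 test recorded on paper only. Table 2 and Appendix D leave Week 6 out.

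A reader might also infer that partial capture weakens the safety check or makes adherence uncheckable. It does neither. The change is declared, every result is on paper source, Protocol 11.1.2 provides for source data verification, and 14.4 requires a pregnancy to be reported within 24 hours of awareness.

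Finally, a flat contrast of 2 doses against 4 would be too strong. It holds only for tests exactly 7 days apart; with one test per study week the contrast is 3 against 4.

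**Conclusion.** The point holds as an inconsistency in current protocol text, with a limited SAP mismatch beside it. A site relying on 7.2.4 alone would do 2 or 3 tests after Day 1 instead of at least 5, and could give up to 4 doses between tests instead of 2 or 3. These counts assume the SAP's nominal dosing days. The count of 6 uncaptured dosing visits, and the placing of Days 15 and 29 in uncaptured weeks, further assume that the Table 1 footnote uses Table 3's week labels.

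The SAP mismatch affects only what the listing can show. No endpoint, estimand or efficacy analysis is touched, so the priority is low. Because 7.2.4 governs continued participation, reconciling it is still more than a clerical correction. Which frequency is right is a clinical matter on which this review takes no position.

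**What to change.** 1. In the protocol, reconcile the schedule table and footnote in 6.1 with 6.2.4.2, 6.2.4.3 and 7.2.4, so that all state one frequency of the sponsor's choosing. Say whether the interval is counted in days or in study weeks, since the two give different maximum gaps.
2. In the SAP, align the Table 1 footnote, the pregnancy-test rows of Table 2, 8.11.3.2 and Appendix D item 10 with that frequency, using one set of week labels.
3. Footnote the pregnancy-test listing (SAP 12.8.5, Layout L13) to say which weeks exist only on paper source.

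The cost is protocol and SAP wording plus one listing footnote. No change to the analysis or the eCRF is needed for this; whether to enter more results is for the sponsor to decide once the frequency is settled.
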